3.6 Exploratory Analyses

Exploratory endpoints include the following:

- Change from baseline in echocardiogram parameters (except GLS) in the Randomized Set, ECHO subgroup and in the CM-ECHO Set
- Change and percent change from baseline in NT-proBNP in the FAS, ECHO subgroup and in the CM-ECHO Set
- Change from baseline in the log-transformed NT-proBNP values in the FAS, ECHO subgroup and in the CM-ECHO Set
- Shift table from baseline in PND score in the FAS and in the PPS
- Change from baseline in NSC total score in the FAS and in the PPS
- Change from baseline in the NSC individual domain scores (muscle weakness, sensory [hypo/loss of sensation], sensory [paresthesia, hyper sensation], autonomic [GI/urinary incontinence], and autonomic [other than GI//urinary incontinence]) in the FAS and in the PPS
- Proportion of patients with at least 60% reduction in TTR in the FAS and in the PPS

Echocardiogram parameters, NSC (total and individual domains), and NT-proBNP (log-transformed) will be summarized and statistically analyzed using the MMRM described in Section 3.3.2. Summary statistics will be used to summarize the other exploratory endpoints.

Note that the 7 point change score (-3, -2, -1, 0, 1, 2, 3) that is recorded on the NSC questionnaire will be listed but not summarised or analysed. Similarly for questions 20-29 the location is only listed. Questions 31-34 are of particular interest and therefore the number and percentage of patients responding 0 (No), 1 (slight +), 2 (moderate ++) or 3 (severe +++) will be presented.

The ECHO data analysis will be conducted by CICL.

Note: retinol and retinyl palmitate are specified as exploratory endpoints in the protocol. These endpoints are considered safety endpoints and therefore will be summarized with safety laboratory parameters.

3.7 Analysis of the PD and Primary Efficacy Endpoints Relationship

The relationship between TTR and both primary endpoints will be explored in the FAS and the PPS among the subset with an assessment within the Week 66 analysis window. For each of the primary endpoints, a scatterplot will be provided with change from baseline to Week 66 in the primary endpoint on the y-axis and change from baseline in TTR on the x-axis. Change from baseline in TTR will be represented by the area under the curve (AUC), and calculated using the following formula

$$\sum_{v=1}^V [(y_v + y_{v-1}) \times (t_v - t_{v-1}) \times 0.5] - y_0 \times (t_V - t_0)$$

where y_v is the TTR concentration from baseline to visit v on day t_v , $v = 0, \dots, V$, with $v = 0$ corresponding to baseline.

A four parameter Emax model will be fit to this data to characterize the relationship. If the Emax model does not converge, other models will be explored.

An additional investigation will be performed based on the categorization of the AUC TTR data. There will be a total of five categories. The first category will include patients in the placebo group. The other categories is for the ISIS 420915 group, where categories are defined based on quartiles of the AUC for change from baseline in TTR. Change for baseline to Week 66 for both primary endpoints will be summarized by TTR category. An analysis of covariance model will be fit with the change from baseline in the efficacy endpoint as the dependent variable, and TTR category, baseline value of the primary endpoint, and randomization factor as explanatory variables. The estimated LS difference between the separate ISIS 420915 TTR categories and the placebo category will be presented.

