3.2.2 Subject Populations Analyzed

The following analysis populations are defined for this study:

- Screened patients will be defined as those patients who signed an informed consent form.
- The Randomized Set will be defined as those screened patients who received a randomization assignment. Results will be summarized under the treatment to which patients were randomized.
- The Full Analysis Set (FAS) will include all randomized patients who received at least 1 injection of Study Drug (ISIS 420915 or placebo) and who have a baseline and at least one post-baseline efficacy assessment for the mNIS+7 score or Norfolk QOL-DN questionnaire total score. This will be the primary population for analysis of efficacy and PD outcomes. Results will be summarized under the treatment to which patients were randomized.
- The Safety Set (SS) will include all randomized patients who received at least 1 injection of Study Drug. This population will be used for analyses of all safety measures. Results will be summarized under the treatment which the patients received.
- The Per-Protocol Set (PPS) will include the subset of the Full Analysis Set who have received at least 80% of the prescribed doses of Study Drug and who have no major protocol violations that would be expected to affect efficacy assessments. Prescribed doses of Study Drug mentioned above is defined as the total assigned dose in mg from the Week 1 to the last dose within this study, i.e. $300\text{mg} \times 67\text{doses} = 20100\text{mg}$. This will be a secondary population for efficacy and PD analyses and will be used for sensitivity purposes. The detailed criteria and definitions for major protocol violations will be specified and finalized prior to unblinding; individual subjects will be identified as meeting the violation criteria or not after locking the database and prior to unblinding. Results will be summarized under the treatment which the patients received.
- PK Set will include all subjects who are randomized and receive at least one dose of active Study Drug (ISIS 420915) and have at least one evaluable PK sample collected and analyzed with reportable result. Results will be summarized under the treatment which the patients received.

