The planned sample size for this study was revised from 195 to 135 using information published from the placebo controlled Phase 3 Diflunisal trial (Berk et al. 2013), a retrospective, multinational natural history study in 283 FAP patients (Adams et al. 2015), and uncontrolled data using another TTR mRNA targeted therapeutic (Adams 2015). It is estimated that the placebo group will have a 16 point increase in the mNIS+7 score from baseline to Month 15, and the treated group will have a 6.4 point increase in mNIS+7. The standard deviation of the change from baseline in each treatment group is estimated to be 14. With 135 patients (2:1 allocation ratio) there would be at least 90% power to detect a 9.6 point difference in the change from baseline in the mNIS+7 score between the 2 groups, with a two-sided t-test of 5% alpha, assuming that the dropout rate is approximately 25%. For the Norfolk QOL-DN questionnaire total score, it is estimated that the placebo group will have a 13.3 point change from baseline to Month 15, the treated group will have a 2.6 point change from baseline and the standard deviation of the change from baseline in each treatment group will be 18. With 135 patients, there would be at least 80% power to detect a 10.7 point difference in the change from baseline in the Norfolk QOL total score between the 2 groups, with a two-sided 5% alpha level, assuming that the dropout rate is approximately 25%.

5 Interim Analyses

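### The pooled Emax curve in SAP 3.7 mainly restates the drug-placebo difference, and nothing planned in that section tests whether more TTR lowering goes with more benefit among treated patients

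*SAP*

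**What the plan says.** SAP 3.7 sets the population first: "The relationship between TTR and both primary endpoints will be explored in the FAS and the PPS among the subset with an assessment" in the Week 66 window. Both sets contain both arms (SAP 3.2.2). For each primary endpoint there is one scatterplot of change to Week 66 against the baseline-corrected area under the TTR curve. The model sentence follows: "A four parameter Emax model will be fit to this data to characterize the relationship". No treatment term, baseline score or stratification factor is named for it. If the fit does not converge, unspecified other models are to be tried.

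The section then plans a second analysis with five categories. Of these, "The first category will include patients in the placebo group". The other four belong to the ISIS 420915 arm, "where categories are defined based on quartiles of the AUC for change from baseline in TTR". An ANCOVA adjusts for the endpoint's baseline value and the randomization factor. Its stated output is: "The estimated LS difference between the separate ISIS 420915 TTR categories and the placebo category will be presented". Outcomes are also summarized by category. No contrast between treated quartiles and no trend test is named.

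**The concern.** The trial has a single active regimen, 300 mg (protocol 3.1). Protocol 2.4 predicts a TTR reduction of about 80% at steady state and gives about 3 months to reach it. Placebo patients should stay near zero. TTR change is then close to a treatment label. A curve through both arms joins two clusters: its height is roughly the randomized difference, and its midpoint and steepness depend on a region with few patients.

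Such a curve cannot by itself separate a drug effect that works by any route from a graded benefit of deeper TTR lowering. The distinction matters because protocol 2.4 says the degree of reduction needed is unknown, and SAP 1.3 makes TTR lowering the mechanism. A fitted TTR-efficacy curve in the study report could be taken as evidence on both.

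**Working it through.** **1. The plan's own figures.** SAP section 4 states: "With 135 patients (2:1 allocation ratio) there would be at least 90% power to detect a 9.6 point difference", with SD 14 and 25% dropout. For Norfolk QOL-DN it gives 10.7 points, SD 18 and at least 80% power. Completers: 45 × 0.75 = 33.75 placebo and 90 × 0.75 = 67.5 active.
- mNIS+7: SE = 14 × √(1/33.75 + 1/67.5) = 2.951. Power = Φ(9.6/2.951 − 1.960) = Φ(1.293) = 90.2%. The noncentral t with 34 and 68 patients gives 89.9%.
- Norfolk: SE = 18 × 0.2108 = 3.795. Power = Φ(10.7/3.795 − 1.960) = Φ(0.860) = 80.5%; noncentral t 80.0%.

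The stated power reproduces. Section 3.7 itself gives no power or alpha.

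**2. TTR assumptions (not in the documents).** If TTR falls linearly to 80% over 3 of 15 months, the time-averaged reduction is 80% × (12 + 1.5)/15 = 72%. I used 65-75% on drug, 0 on placebo and a between-patient SD of 10-25 percentage points in each arm. TTR is expressed as fractional change, whereas the SAP's AUC is in concentration-time units.

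**3. Why pooling creates a slope.** Suppose outcome is unrelated to TTR inside each arm. With treated fraction p = 2/3, arm separation d and within-arm TTR SD σ, a pooled straight line drops over the distance d by

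Δ × p(1−p)d² / [p(1−p)d² + σ²].

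- d = 0.75, σ = 0.10: 9.6 × 0.125/0.135 = 8.9 points.
- d = 0.65, σ = 0.25: 9.6 × 0.0939/0.1564 = 5.8 points.

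So 60-93% of the planned difference appears as a TTR slope when the true within-arm slope is zero.

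**4. Simulation of the planned curve.** 3000 trials per row, 34 placebo and 68 treated, no within-arm link, without the baseline and strata covariates. Results are among trials significantly favouring drug. The Emax test is a 3-df F test against a flat line at 0.05. I added that test; the SAP attaches none.

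| Endpoint; mean TTR reduction/SD | Curve falls | Median fall (points) | Emax significant | Pooled linear significant | Linear with arm term | Treated-only linear | Quartiles differing from placebo (of 4) |
|---|---|---|---|---|---|---|---|
| mNIS+7; 75/10 | 99.9% | 10.8 | 82.6% | 96.2% | 4.6% | 4.6% | 2.75 |
| mNIS+7; 75/15 | 99.9% | 10.9 | 81.7% | 92.9% | 4.2% | 4.4% | 2.73 |
| mNIS+7; 75/20 | 99.9% | 10.7 | 78.3% | 87.3% | 4.9% | 5.0% | 2.74 |
| mNIS+7; 65/25 | 99.7% | 9.9 | 66.2% | 75.1% | 5.2% | 4.9% | 2.72 |
| Norfolk; 75/15 | 99.9% | 12.8 | 73.0% | 88.4% | 5.0% | 5.6% | 2.41 |

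With no treatment effect (75/15), the pooled Emax was significant in 2.9% of all trials, so the signal comes from the arm contrast.

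**5. The quartile contrasts.** Each treated quartile holds about 68/4 = 17 patients. For mNIS+7, SE against placebo = 14 × √(1/17 + 1/34) = 4.16. The chance that one contrast is significant is Φ(9.6/4.16 − 1.96) = Φ(0.348) = 64%, or about 2.5 of 4 over all trials. The simulation gave 2.50-2.52 over all trials and 2.72-2.75 in positive ones. With no gradient among treated patients, most quartiles will therefore still beat placebo. The four quartile means fell in TTR order in about 4-5% of positive trials, as chance predicts (1/24 = 4.2%). A linear trend across them was significant in 4.6-5.9%.

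**The case against.** The strongest reply is that SAP 3.7 already contains the better analysis. The quartile ANCOVA keeps placebo apart, splits treated patients by achieved TTR change and adjusts for covariates. A reader who lines up the four differences from placebo would usually see no ordered pattern if none exists. That stands, and the section as a whole cannot be said to add nothing to the primary contrast. What remains is that the comparison among treated quartiles is left to the eye, with no estimate or interval.

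Second, the section is exploratory, with no alpha or decision attached, and the dose rationale in protocol 2.4 rests on Phase 1 data. This limits the weight of the point. Third, pooling is inferred: the SAP does not say so in terms. It is still the natural reading, because the same section separates the arms explicitly when it wants to.

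Fourth, placebo patients anchor the zero-reduction end of the curve. If TTR is the mediator, an arm term would remove much of a real effect. This is a good reason not to force an arm term into the pooled curve or to discard it. Fifth, the SAP provides for non-convergence, so failed fits are not a defect in themselves.

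A reader might go further and infer that any positive trial must produce a TTR exposure-response. The documents and the numbers do not support that. The direction of the curve is nearly assured, but a clear departure from flat appears in 66-83% of positive mNIS+7 trials under the assumed spreads, and SAP 3.7 declares no significance for the curve.

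**Conclusion.** The point holds in limited form. On the natural reading, the Emax fit pools two well-separated arms without a treatment term. In most positive trials it would then mainly restate the randomized difference, and it cannot by itself show that deeper TTR lowering brings more benefit. The quartile ANCOVA partly answers this, but its stated contrasts are all against placebo, and on average 2.7 of 4 (2.4 for Norfolk) would be significant in a positive trial with no gradient among treated patients.

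The size rests on assumed TTR means and SDs. A wider spread weakens the artefact (83% down to 66%) without removing it. The primary inference is unaffected.

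**What to change.** In SAP 3.7:

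- Keep the pooled scatterplot and Emax curve as descriptive displays, with points marked by arm.
- Add a linear or simple spline TTR term fitted within the ISIS 420915 arm, adjusted for baseline score and the three stratification factors. Report the slope with its 95% CI.
- Add a linear trend contrast across the four treated quartiles to the planned ANCOVA.

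This needs SAP wording and a little programming, and no new data. The real cost is precision. With 68 treated patients and SD 14, the slope's SE is 14/(σ√67). Per 10 percentage points of TTR reduction that is 1.71 points at σ = 0.10 and 0.68 at σ = 0.25, giving 95% half-widths of about 3.4 and 1.4 points. A benefit proportional to TTR lowering would be 9.6/7.5 = 1.3 points per 10 at a 75% mean reduction, or 9.6/6.5 = 1.5 at 65%, so the result may well be inconclusive. The comparison is also non-randomized: achieved TTR reduction may track adherence, dose pauses or antibodies. Report it as exploratory, with that caution stated.

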2.4 Rationale for Dose and Schedule of Administration

The pharmacokinetics and disposition of many drugs in this class have been characterized and there are remarkable similarities from sequence to sequence and across species. Because distribution to tissues is the dominant mechanism for plasma clearance, it can be assumed that plasma pharmacokinetic similarities translate into similarities in tissue distribution. This assumption is supported by the knowledge that patterns of tissue distribution for oligonucleotides are similar in mice, rats, rabbits, dogs and monkeys (and thus are expected to be similar in humans). Additionally, ASOs are hydrophilic and distribute predominantly to the lean body mass and in our experience they should be administered as a fixed dose, rather than by total body weight.

In FAP (and FAC), both wild-type and mutant TTR protein will deposit in tissue as amyloid. However, it is not known what degree of reduction of TTR will be required to optimally attenuate progression of disease. TTR mutant reductions $\geq 90\%$ have been observed post-liver transplantation (Adams et al. 2000) and have been shown to have a therapeutic effect. Therefore, the therapeutic goal for ISIS 420915 is to reduce both wild-type and mutant plasma TTR levels as much as possible using a dose level that will not cause unacceptable toxicity. Based on data from the TTR knock-out mouse (Episkopou et al. 1993) and from our 9-month chronic toxicology studies in non-human primates, significant target related toxicities are not anticipated even with near complete reduction of TTR. In the ISIS 420915 Phase 1 study, the 300 mg dose level showed a satisfactory safety profile and a substantial pharmacodynamic effect after 6 doses ($> 70\%$ mean reduction in plasma TTR levels). The PD effect observed with the 300 mg dose level was also similar to that observed with the 400 mg dose level, and therefore the 300 mg per week dose (with additional loading doses in the first week) was selected for this Phase 2/3 study. Preliminary PK/PD modeling (based on data from the Phase 1 study and extrapolation to steady-state) predicts mean total (wild-type and mutant) TTR steady state reductions of $\sim 80\%$ with either a 300 mg/wk or 400 mg/wk regimen.

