3.4.2 Pharmacodynamic Endpoint Definitions

Pharmacodynamic endpoints are:

- Change and percent change from baseline to Week 65 in TTR level
- Change and percent change from baseline to Week 65 in RBP4 level.

Analyses of the pharmacodynamic endpoints will be evaluated using the same method as the primary efficacy analysis (MMRM described in Section 3.3.2). All pharmacodynamic analyses will be conducted on both the FAS and the PPS.

In addition the proportion of subjects with percentage decrease from baseline in plasma transthyretin (TTR) $\geq 60\%$ will be summarized by treatment group at each visit.

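### SAP 3.7 ranks treated patients by absolute AUC change in TTR without adjusting for baseline TTR, so the response quartiles partly, and possibly mostly, reflect entry TTR

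*SAP*

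**What the plan says.** SAP 3.7 is exploratory: "The relationship between TTR and both primary endpoints will be explored in the FAS and the PPS", restricted to patients "among the subset with an assessment within the Week 66 analysis window". The exposure measure is introduced with "Change from baseline in TTR will be represented by the area under the curve (AUC), and calculated using the following formula". The formula is the trapezoidal sum of TTR over visits minus y0 × (tV − t0), "where y_v is the TTR concentration from baseline to visit v on day t_v". The result is in concentration × days. It is divided neither by baseline TTR nor by time, and the last visit V is not specified.

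This AUC is the x-axis of the scatterplots and the input to a four-parameter Emax model, for which no covariates are named. It also forms five categories: placebo, and four groups of treated patients whose "categories are defined based on quartiles of the AUC for change from baseline in TTR". The ANCOVA uses "TTR category, baseline value of the primary endpoint, and randomization factor as explanatory variables", and each treated category is compared with placebo. Baseline TTR does not appear.

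Elsewhere TTR is handled on both scales. Protocol 10.1.2.2 states the PD endpoint as change from baseline. SAP 3.4.2 has "Change and percent change from baseline to Week 65 in TTR level" and a summary of patients with at least a 60% fall. Protocol 2.4 "predicts mean total (wild-type and mutant) TTR steady state reductions of" about 80%.

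**The concern.** If percent reduction is fairly similar between patients, absolute change is close to a constant times baseline TTR. The top quartile then tends to contain patients who entered with high TTR, not those in whom the drug worked best. A patient can fall in a larger-reduction group while keeping more circulating TTR than a patient in a smaller-reduction group.

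Two consequences follow. Relative response is misclassified, which blurs a real gradient. And if entry TTR is itself related to progression, each quartile enriched for high or low entry TTR is compared, unadjusted, with a placebo group of average entry TTR. The differences could then create or hide a gradient that readers would take as evidence that more TTR lowering gives less progression.

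**Working it through.** **Planning inputs.** SAP 3.7 states no figure of its own. Protocol 10.2 and SAP section 4 give 135 patients, 2:1, SD 14, difference 9.6 and 25% dropout. That leaves 67.5 treated and 33.75 placebo patients, and about 17 per treated quartile. Check of the stated power: SE = 14 × √(1/67.5 + 1/33.75) = 2.95; 9.6/2.95 = 3.25; Φ(3.25 − 1.96) = 0.90, which agrees with the plan's 90%.

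**1. What the AUC measures.** Write TTR at visit v as y0 × (1 − r × f_v), where r is the steady-state fractional reduction and f_v rises from 0 to 1. The formula reduces to

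AUC change = −y0 × r × k × (tV − t0),

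where k is the time average of f. On the protocol's PD days 1 to 449, tV − t0 = 448. An 80% reduction, approached over the stated three months or so, gives a relative AUC of −0.753, so k = 0.753/0.80 = 0.941. Entry values below are illustrative.

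| Entry TTR | Reduction | AUC change | Residual TTR |
|---|---|---|---|
| 15 | 80% | −5061 | 3.0 |
| 20 | 80% | −6748 | 4.0 |
| 25 | 80% | −8435 | 5.0 |
| 30 | 80% | −10122 | 6.0 |
| 18 | 85% | −6452 | 2.7 |
| 30 | 60% | −7591 | 12.0 |

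The first four patients respond identically but are spread out by entry level. The last ranks above the fifth with a weaker percent response and over four times the residual TTR.

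**2. How much of the ranking is entry TTR.** The documents give no spread for baseline TTR or percent reduction, so a grid was assumed: baseline CV 15, 25 or 35%; mean reduction 70, 75 or 80%; SD of reduction 5, 10, 15 or 20 points (36 sets). The R² of the AUC with baseline TTR runs from 0.21 to 0.97, and with percent reduction from 0.03 to 0.77. Baseline TTR has the larger share in 27 of 36 sets. The other nine combine a reduction SD of 15–20 points with baseline CV 15%, or 20 points with CV 25%; one of these is nearly a tie (0.48 against 0.49).

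**3. Size of a false gradient in mNIS+7.** Let ρ be the assumed correlation of baseline TTR with mNIS+7 change after the model's covariates, and c the correlation of the AUC with baseline TTR. The mean of an outer quartile of a normal variable is 1.27 SD from centre. Because placebo patients should have average entry TTR,

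bias of an extreme quartile against placebo = 1.27 × 14 × ρ × c.

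Take c = 0.78 to 0.93 (baseline CV 20–30%, reduction mean 75%, SD 8–12 points):
- Low: 1.27 × 14 × 0.1 × 0.78 = 1.4 points.
- High: 1.27 × 14 × 0.3 × 0.93 = 5.0 points.
- Top against bottom quartile is double: about 2.8 to 9.9 points.

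For scale, the SE of a quartile against placebo is about 14 × √(1/17 + 1/34) = 4.2 points, and between two quartiles 14 × √(2/17) = 4.8 points.

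**4. False-trend rate.** In simulations with 67 treated patients, SD 14 and no effect of percent reduction, a 5% test for trend across the quartiles rejected as follows.

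| ρ | As written |
|---|---|
| 0 | 4.7–5.7% |
| 0.1 | 6–11% |
| 0.2 | 13–28% |
| 0.3 | 20–56% |

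At every ρ tried (0 to 0.4), percent-scaled quartiles gave 4.4–5.8%, and the absolute AUC with baseline TTR as covariate gave 4.5–6.7%. SAP 3.7 specifies no trend test; these rates only gauge how often a gradient would look convincing.

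**5. Follow-up time.** With a Day 449 ± 5 visit, time accounts for 0–0.2% of the log-variance of the AUC. Spread over Day 411–501 (the Week 66 window in the DSMB SAP; the main SAP's window is redacted), it is 2–11%. If the last TTR sample is Day 407 rather than 449, the AUC shrinks by about 10%.

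**The case against.** The strongest reply is that absolute lowering is a legitimate exposure. SAP 1.3 frames the hypothesis as reducing the amount of circulating TTR, and the protocol's PD endpoint is absolute change. Percent change is not free of baseline either: SAP 5.1 anticipates values below quantification, which caps the measurable percent fall in patients with low entry TTR. This stands, so the choice of scale is partly preference. It does not answer the missing covariate, nor the table's last two rows, where the larger absolute reduction goes with far more TTR left in circulation.

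Second, a reader might infer that the quartiles mostly rank entry TTR. The documents give only a mean reduction, no spreads, and nine of the 36 assumed sets go the other way.

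Third, a reader might argue that entry TTR must be prognostic because TTR is pre-albumin (SAP 2.5.2) and malnutrition is a cause of death in this disease (Protocol 2.1.1). Neither document says that entry TTR tracks nutrition or predicts the primary endpoints. Baseline score and randomization factors are already in the model, so only a residual correlation counts, and at zero there is no false trend.

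Fourth, this is not the plan's only look at mechanism. SAP 3.8.1.2 allows exposure-response exploration with PK measures, and 3.8.2 stratifies TTR and both primary endpoints by immunogenicity status. Section 3.7 carries no alpha or decision rule.

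Fifth, the Emax fit is not limited to treated patients, so much of its x-axis spread is placebo against drug. The quartile calculations above do not describe it.

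**Conclusion.** The point holds as a weakness of an exploratory analysis. The metric contains baseline TTR and the ANCOVA does not adjust for it, so the quartiles partly, and possibly mostly, reflect entry TTR rather than relative suppression. A false gradient needs a further condition that the documents do not establish: a relation between entry TTR and outcome beyond baseline score and strata. On assumed correlations of 0.1 to 0.3 the bias in the contrast the SAP reports, quartile against placebo, is about 1.4 to 5 points of mNIS+7. At its upper end this is about one standard error; at its lower end it is lost in noise. Top against bottom it is about 3 to 10 points. With no such relation the harm is misclassification only. The spreads and correlations are all assumptions.

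A reader might also infer that the missing division by time is a major fault, or that the trial's main result is at risk. The restriction to patients with a Week 66 assessment keeps the time effect small, and the primary MMRM, its testing order and its type I error do not use this analysis. The change is a nearly free improvement.

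**What to change.** In SAP 3.7:
- Add baseline TTR as a covariate in the ANCOVA, and in the Emax model where it can be fitted.
- Repeat the scatterplot and quartile analysis with the AUC change divided by y0 × (tV − t0), the time-averaged percent change, alongside the absolute AUC.
- State which TTR visit is V.

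The cost is SAP wording, one derived variable and one more display; all inputs are already collected. Quartile contrasts on the absolute AUC become less precise because the AUC is collinear with baseline TTR. In a check with 68 treated patients in four quartiles, 34 placebo, mean reduction 75% and four pairs of spreads (reduction SD 10–20 points, baseline CV 15–35%), the SE against placebo rose from 4.2 to between 4.4 and 4.9 points, and top against bottom from 4.8 to between 5.2 and 6.5. The percent-scaled version does not have this collinearity when percent reduction is unrelated to entry TTR, which is a reason to show both.
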